- 4) To determine quality of life (QoL) at baseline and at 3, 6, 9 and 12 months following treatment using the EORTC QLQ-C30 instrument combined with the EORTC QLQ-H&N35 module. The main scores of interest at each time point will be the global QoL scale and the individual scales for dry mouth, oral pain, swallowing, opening mouth, sticky saliva, and social eating.
- 5) To correlate NTCP values with change in QoL results.

STUDY POPULATION

Research subjects will be recruited from the Radiation Oncology clinic on the UAMS campus. The potential research subject will be identified by the physician during their routine clinic visit. Prior to any research activities, the subject will be approached for participation in the study by their physician or staff member, who will discuss the protocol along with the risks and potential benefits of participating in it. Subjects currently taking saliva stimulating drugs will be asked if they are willing to discontinue such drugs in order to participate. A clear statement will be made concerning the voluntary nature of participation and that the decision will have no effect on their remaining care.

We plan to consent up to 75 subjects in order to reach our maximum accrual of 50 subjects, randomized to the two study arms. Eligibility waivers are not permitted. Subjects must meet all of the inclusion and exclusion criteria to be enrolled in the study. Study procedures may not begin until a subject is consented.

Inclusion criteria

1. Histological documentation of HN-SQCC
2. Older than 21 years of age
3. Subject is eligible for routine chemo-radiotherapy for treatment of HN-SQCC
4. Informed consent is obtained
5. Karnofsky performance status of at least 70 points

Exclusion criteria

1. Women with a positive urine pregnancy test are excluded from this study; women of childbearing potential (defined as those who have not undergone a hysterectomy or who have not been postmenopausal for at least 24 consecutive months) must agree to refrain from breast feeding and practice adequate contraception
2. Unable to comply with study procedures

3. Use of saliva stimulating prescription drugs such as Evoxac or Salagen

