The use of saliva stimulating drug shave the potential of confounding the degree of xerostomia experience by the subject due to radiotherapy. Because of this, these type of drugs are not allowed during the duration of the subject's participation in the clinical trial. Symptomatic relief of xerostomia will be approached using medications that do not stimulate the production of saliva. Such drugs include artificial salivas and Biotene oral spray. Potential subjects who are currently using saliva stimulating drugs must discontinue the drugs to qualify for the study. A washout period of 3-5 days is required.

4. Unable to receive standard chemotherapy

INVESTIGATIONAL PLAN

Upon consenting to the study, the subject will complete a series of questionnaires, including the subjective LENT/SOMA xerostomia form, the University of Michigan's XQ, and the EORTC QLQ-C30 and H&N35 modules. Then the subject will attend their scheduled routine chemotherapy as prescribed by the treating medical oncologist. This will be given concurrently with radiation therapy as discussed with the Radiation Oncologist.

Following the completion of the scheduled chemo-radiotherapy, the subject will be seen in Radiation Oncology every 3 months for routine follow-up visits related to their radiation treatment. During those visits, the subjects will once again complete the packet of questionnaires. The EORTC questionnaires and the xerostomia assessments (the LENT/SOMA form and the XQ) will also be filled out at 3 months (+/- 30 days), 6 months (+/- 30 days), 9 months (+/- 30 days) and 12 months (+/- 30 days) after chemo-radiotherapy. The packet will be completed in the clinic, but if necessary can be sent home with the subject with a return envelope, emailed to the subject, or the subject may be called to respond to the questions over the phone. The subject is also to be seen at the discretion of the medical oncologist and surgeon as part of routine oncologic follow-up.

Duration of follow-up

The subject will not be followed after the completion of the questionnaires at the 12 month visit.

Removal of subject from study

Subjects will be removed from the study when any of the criteria listed below apply:

- Subject withdraws consent from study;
- Subject is unable to comply with protocol requirements;
- Subject experiences toxicity that makes continuation in the protocol unsafe;
- Treating physician judges continuation on the study would not be in the subject's best interest;

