Quality of Life: The European Organisation for Research and Treatment of Cancer (EORTC) QLQ-C30 [27] is a widely used core module, designed to capture multidimensional aspects of health-related quality-of-life across a wide spectrum of different malignancies. It generates a global score, 5 functional scores, and 9 symptom scores. The H&N35 module [28] assesses concerns specific to head-and-neck cancer patients; it yields 18 symptom scores. Scores on both modules are transformed to a 0-100 scale, with higher scores representing more favorable outcomes on the functioning scales but poorer outcomes on the symptom and head-and-neck-specific scales. In the current study, scales of special interest include dry mouth, oral pain, swallowing, opening mouth, sticky saliva, social eating, and global QOL. Evidence supports the reliability and validity of the EORTC scales [27-29].

Demographic and Clinical Characteristics: Demographic information will be collected at the baseline assessment to record basic background information (e.g., age, race, gender, education, comorbidities, etc.). Clinical variables will be obtained from the treatment team or medical record (e.g., stage, site, recurrence status, prior treatments, time since diagnosis, etc.).

ADVERSE EVENTS

Adverse events associated to study participants

The potential risk to study participants is the potential for loss of confidentiality. Measures to protect the confidentiality of study participants will be implemented as described in the Data Handling and Recordkeeping section.

There will be no direct benefits to the study participants; however, knowledge gained from the study could potentially benefit patients in the future.

Adverse event monitoring

Adverse event data collection and reporting, which is required as part of every clinical trial, is done to ensure the safety of subjects enrolled in the studies as well as those who will enroll in future studies using similar agents. Adverse events are reported in a routine manner at scheduled times during a trial. Additionally, certain adverse events must be reported in an expedited manner to allow for optimal monitoring of subject safety and care.

All subjects experiencing an adverse event will be monitored until the completion of the subject's post-radiotherapy visit:

- the adverse event resolves or the symptoms or signs that constitute the adverse event's return to baseline;

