This study also has the following secondary objectives:

- 1) To compare descriptively the arm treated with IMRT under the margin-based radiotherapy plan to the arm treated with IMRT under the robust radiotherapy plan for possible differences in derived outcomes of interest, including but not limited to: (1) occurrence rate of grade ≥ 2 xerostomia as determined using the LENT/SOMA scale; and (2) occurrence rate of overall score ≥ 30 on the XQ.
- 2) To obtain NTCP values of the parotid glands from both margin-based and robust radiotherapy treatment plans using validated parameter values of the NTCP mean dose model. Each subject will have their parotid NTCP values computed under both plans, even though they will receive IMRT delivered under only the plan they are randomized to.
- 3) To obtain dose statistics for dose delivered to the parotid glands from both margin-based and robust treatment plans.
- 4) To determine quality of life (QoL) at baseline and at 3, 6, 9 and 12 months after treatment using the EORTC QLQ-C30 instrument combined with the EORTC QLQ-H&N35 module. The main scores of interest at each time point will be the global QoL scale and the individual scales for dry mouth, oral pain, swallowing, opening mouth, sticky saliva, and social eating.
- 5) To correlate NTCP values with change in QoL results.

To accomplish this study's secondary objectives, the analysis will proceed as follows:

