- 1) Xerostomia grades from the LENT/SOMA scale will be dichotomized as grade ≥ 2 versus grade < 2 , then summarized by treatment arm and time point as the number and proportion achieving grade ≥ 2 . The dichotomization is placed at grade $</\geq 2$ because that was the cutpoint used in the PARSPORT study [22], but we will also consider an alternative dichotomization at grade $</\geq 3$. As for the overall XQ score (a continuous variable), we will dichotomize it at different cutpoints chosen for their potential clinical relevance, beginning with a cutpoint of $</\geq 30$, then summarize the result by treatment arm and time point as the number and proportion of subjects who surpass the cutpoint. For all dichotomized versions of both xerostomia measures, the proportions on each arm and proportion differences between treatment arms will be estimated at each time point. Estimated proportions and their differences will be accompanied by two-sided 90% confidence intervals. Exploratory mixed-models analysis may be used in follow-up mode, as time permits, to explore more deeply the differences between treatment arms and how they change over time.
- 2) NTCP values from both plans will be summarized by plan and treatment arm as the mean, SD, median, quartiles, and range. Data will be graphed using box plots versus treatment arm. Plans will be compared descriptively by calculating the paired difference between them, and summarizing the result as means, SDs, and ranges. Means will be accompanied by 90% confidence limits.
- 3) Dose statistics on each subject (i.e., the mean, SD, median, 1st and 3rd quartiles, 5th percentile, and 95th percentile of dose received by the subject) will be summarized by statistic and treatment arm as the mean, SD, median, quartiles, and range. Data for each statistics will be graphed using box plots versus treatment arm.
- 4) The global EORTC QOL scale and individual scales for dry mouth, oral pain, swallowing, opening mouth, sticky saliva, and social eating will be summarized by treatment arm and time point as the mean, SD, and range, and also (for individual Likert-scaled items that have 5 or fewer ordered categories) as the

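### Secondary objective 1 is worded as an occurrence rate but analyzed as prevalence in all subjects, so xerostomia present before radiotherapy counts in the post-treatment rates; new-onset rows should be added.

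*Combined protocol and SAP*

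**What the plan says.** The primary objective concerns the prevalence and grade of xerostomia over time. Secondary objective 1 uses a different term. It compares the arms on the "occurrence rate of grade ≥ 2 xerostomia as determined using the LENT/SOMA scale" and the "occurrence rate of overall score ≥ 30 on the XQ".

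The analysis of that objective, under Statistical Considerations, dichotomizes each measure. The LENT/SOMA grade is "summarized by treatment arm and time point as the number and proportion achieving grade ≥ 2". For the XQ the plan will "summarize the result by treatment arm and time point as the number and proportion of subjects who surpass the cutpoint". For all the dichotomies, "the proportions on each arm and proportion differences between treatment arms will be estimated at each time point", with two-sided 90% confidence intervals. The plan gives no definition of a new case, no restriction to subjects below the cutpoint at baseline, and no baseline adjustment. Mixed models are optional for this objective, as time permits, and no baseline term is named. Change from baseline is specified only for quality of life (secondary objective 5).

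On who may enter, the disease-related inclusion criteria are histologically documented disease and "Subject is eligible for routine chemo-radiotherapy for treatment of HN-SQCC". Exclusion criterion 3 bars use of saliva-stimulating drugs during the study but adds: "Potential subjects who are currently using saliva stimulating drugs must discontinue the drugs to qualify for the study". A 3-5 day washout applies. No criterion refers to baseline xerostomia, recurrent disease or earlier radiotherapy. Under Measures, the clinical variables to be recorded include "stage, site, recurrence status, prior treatments, time since diagnosis, etc". Both xerostomia forms are completed before radiotherapy and at 3, 6, 9 and 12 months after it.

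**The concern.** An occurrence rate after treatment is naturally read as the share of subjects who develop the condition. The specified calculation gives the share who have it at the visit, whenever it began. A subject at grade 3 before radiotherapy who stays at grade 3 is counted at every later visit, although the planning method cannot have caused that grade. The LENT/SOMA item runs from 1 to 4, so grade ≥ 2 is only one step above the form's minimum.

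The estimates are the pilot's product: the protocol says they will inform the design of larger comparative studies. If a later team reads the all-subject rate as a new-onset rate, it will plan on an event rate that is too high and, where baseline cases persist in both arms, on an arm difference that is too small.

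**Working it through.** **The plan's own figures.** With 25 per arm and 17% loss, the expected number at 12 months is 25 × 0.83 = 20.75, and the binomial probability of 18 or more is 0.9505, as stated. The standard errors of 10%, 30% and 50%, from √(p(1−p)/n), are 6.0, 9.2 and 10.0 points at n = 25 and 7.1, 10.8 and 11.8 points at n = 18. All reproduce. They take every remaining subject as the denominator.

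**Set-up.** Let b be the proportion at or above the cutpoint at baseline, s the proportion of those still there at the visit, and p the new-onset rate among the rest. Then:

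- all-subject proportion = b·s + (1−b)·p
- arm difference = (1−b)·(p₁ − p₂) + b·(s₁ − s₂)

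With equal persistence in the two arms, the second term vanishes and the new-onset difference shrinks by the factor (1−b).

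**Assumptions.** The documents give none of b, s or p. For illustration: b = 10%, 20% or 30%, s = 1 in both arms, and new onset of 50% (margin-based) and 30% (robust), a difference of 20 points. At b = 20%: 0.2 + 0.8 × 0.5 = 0.60 and 0.2 + 0.8 × 0.3 = 0.44.

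| b | All-subject rates | Difference | Baseline-free n per arm at 12 months |
|---|---|---|---|
| 10% | 55% v 37% | 18 points | 20.75 × 0.9 = 18.7 |
| 20% | 60% v 44% | 16 points | 20.75 × 0.8 = 16.6 |
| 30% | 65% v 51% | 14 points | 20.75 × 0.7 = 14.5 |

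The all-subject rate exceeds the new-onset rate by 5 to 15 points in the first arm and 7 to 21 points in the second. With s = 0.8 in both arms the rates are 53% v 35%, 56% v 40% and 59% v 45%, and the differences are unchanged.

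**Precision cost of restricting to baseline-free subjects.** The SE of a difference is √[(p₁(1−p₁) + p₂(1−p₂))/n].

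- b = 10%: all subjects √(0.4806/20.75) = 15.2 points; restricted √(0.46/18.675) = 15.7; about 3% larger.
- b = 20%: √(0.4864/20.75) = 15.3; restricted √(0.46/16.6) = 16.6; about 9% larger.
- b = 30%: √(0.4774/20.75) = 15.2; restricted √(0.46/14.525) = 17.8; about 17% larger.

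**The case against.** The strongest reply is that nothing planned is invalid. Several parts of it stand.

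- **Bias.** A reader might infer that counting baseline cases biases the arm comparison. It does not. Under randomization the all-subject difference is an unbiased contrast for the enrolled population; the new-onset difference is a different estimand. If a later trial keeps similar eligibility and the same endpoint, the all-subject rates are the right planning inputs.
- **Chance imbalance.** A reader might add it as a further error, since at 20.75 per arm the SD of the difference in baseline prevalence is √(2b(1−b)/20.75) = 9.3, 12.4 or 14.2 points for b = 10%, 20% or 30%. That variation is already part of the sampling variance of the difference, so the planned 90% interval covers it.
- **Visibility of baseline.** The proportions are to be estimated at each time point, and the forms are completed before radiotherapy. The natural reading is that the tables include a baseline row by arm.
- **Size.** The shrinkage of 2 to 6 points is small beside a 90% half-width of about 1.645 × 15.3 = 25 points, in a descriptive pilot with no test or decision rule.
- **Who enters.** The documents permit entry with existing dry mouth but do not say that many such patients, or any previously irradiated ones, are expected.

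What does not stand is that the planned output already answers the question. Marginal baseline and 12-month proportions cannot show which subjects are new cases; that needs cross-classification within subject. Subtracting the margins also mixes about 25 subjects at baseline with about 21 at 12 months. The optional mixed models do not fill the gap. Relabeling alone would cure the wording but leave the occurrence rate named in the objective unestimated.

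**Conclusion.** The mismatch between objective and analysis is certain on the text: the label is occurrence, the calculation is point prevalence, and eligibility does not exclude pre-existing cases. Any baseline case that persists is counted in the post-treatment rate. That rate exceeds the new-onset rate whenever baseline cases persist more often than new cases arise (s > p), and the arm difference is reduced when persistence is similar in the two arms.

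The size is unknown because no baseline prevalence is given. Under the assumed 10-30% with full persistence, a 20-point new-onset difference would appear as 18 to 14 points. If few subjects enter with xerostomia, the effect is negligible; if planning method affects persistence, the difference could move either way.

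The documents do not support the stronger readings that the randomized comparison is biased, that its interval is too narrow, or that the entry criteria must change. The prevalence objective is correctly served by the all-subject proportions. This is an inexpensive improvement to a descriptive analysis, not a defect that invalidates it.

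**What to change.** In the analysis of secondary objective 1:

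1. Keep the all-subject proportions, label them prevalence, and state that the baseline row is shown by arm.
2. For each cutpoint, add the proportion newly at or above it among subjects below it at baseline, with n, arm difference and 90% confidence interval at each post-treatment visit, especially 12 months.
3. Add an arm difference adjusted for baseline status that uses all subjects, so that those with baseline xerostomia still contribute.
4. In the precision statement, note the smaller denominator of the new-onset rows.

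The cost is a few table rows from data already collected. The downside is precision: the new-onset rows would rest on about 18.7, 16.6 or 14.5 subjects per arm at 12 months under an assumed 10%, 20% or 30% baseline prevalence, with the SE of the difference up to about 17% larger at 30%. They also say nothing about persistence or recovery in subjects with baseline xerostomia, which is why items 1 and 3 should stand beside them. No eligibility change is needed.

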All other adverse events, such as those that are expected, or are unlikely or definitely not related to the study participation, are to be reported annually as part of regular IRB continuing review.

STATISTICAL CONSIDERATIONS

This is a randomized, two-arm, open-label pilot clinical trial conducted in subjects with squamous-cell carcinoma of the head and neck. Its primary objective is to evaluate descriptively over time the prevalence and grade of xerostomia in subjects treated with IMRT under either biologically optimized margin-based or robust photon radiotherapy of HN-SQCC. Xerostomia will be measured in study subject using two patient-reported scoring systems completed by each subject before radiotherapy and 3, 6, 9, and 12 months after radiotherapy: the LENT/SOMA grading system and the University of Michigan's Xerostomia Questionnaire (XQ; see Eisbruch *et al.* 2001).

To accomplish this study's primary objective, the analysis will proceed as follows: To analyze the XQ, scores on its 8 items will be summed for each subject at each time point to produce an overall XQ score whose values theoretically can range from 0 to 80; it will be treated as a continuous variable. LENT/SOMA grades as written on the form will simply be recorded electronically, and non-integer grades will be allowed if that's what the subject wrote on the form. Longitudinal LENT/SOMA grades will be summarized by treatment arm and time point as the number and proportion of subjects achieving each grade, and also as the mean and SD of grade. Longitudinal overall XQ scores will be summarized by treatment arm and time point as the mean, SD, median, quartiles, and range. Both the correlation between xerostomia measures within each time point and the correlation within each xerostomia measure across time points will be studied using Spearman correlation analysis. Estimated means, SDs, medians, and quartiles will be accompanied by 90% confidence intervals. In exploratory analysis,

we will employ mixed-models analysis to investigate more deeply the interrelationships among the xerostomia measures between treatment arms and time points. Also in exploratory analysis to accomplish the primary objective, we will use means, SD, and ranges to summarize each of the 8 individual items from the XQ by treatment arm and timepoint, and investigate using mixed-models approaches to compare the XQ items descriptively for treatment-arm differences over time.

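### The overall XQ score has no planned arm difference in means with a 90% interval; outside exploratory models, its only interval-backed arm contrasts are proportions at cutpoints, and those after 30 are unlisted

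*Combined protocol and SAP*

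**What the plan says.** **Primary-objective analysis (Statistical Considerations).** The eight XQ items are summed to an overall score whose "values theoretically can range from 0 to 80; it will be treated as a continuous variable". "Longitudinal overall XQ scores will be summarized by treatment arm and time point as the mean, SD, median, quartiles, and range". "Estimated means, SDs, medians, and quartiles will be accompanied by 90% confidence intervals". These are summaries of each arm. The same paragraph adds, as exploratory work, that "we will employ mixed-models analysis to investigate more deeply the interrelationships among the xerostomia measures between treatment arms and time points", and that mixed models will also be explored for the individual XQ items.

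**Analysis of secondary objectives, item 1.** For the overall XQ, "we will dichotomize it at different cutpoints chosen for their potential clinical relevance". The first cutpoint is 30, which secondary objective 1 also names. No further values, number of cutpoints or time for fixing them is given. For the dichotomized versions of both xerostomia measures, "the proportions on each arm and proportion differences between treatment arms will be estimated at each time point", with two-sided 90% intervals. Further mixed modelling under this item is optional.

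**Analysis of secondary objectives, item 4.** For the EORTC scales, arm differences in means are to be estimated at each time point with two-sided 90% intervals. The sentence sits under the quality-of-life item and does not clearly extend to the XQ.

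**Purpose.** The objective is "To compare descriptively the arm treated with IMRT under the margin-based radiotherapy plan to the arm treated with IMRT under the robust radiotherapy plan". No test, alpha or decision rule is attached. The results are meant to inform the design of larger studies.

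**The concern.** The XQ is one of the two measures behind the primary objective, and the plan treats it as continuous. Yet it gets a weaker arm contrast than the secondary EORTC scales, whose mean differences come with intervals. With 25 subjects per arm, and possibly 18 at 12 months, the precision of a contrast matters.

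The cutpoints raise a second, smaller issue. For LENT/SOMA the plan takes its cutpoint from a previous trial and names one alternative. For the XQ the set is open after 30. The trial is open-label, and nothing requires later cutpoints to be fixed before results by arm are seen. If a cutpoint were later adopted for a larger trial because it separated the arms well here, the effect carried into that design would be too large. That is true whether or not a test is attached.

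**Working it through.** **1. The plan's own precision figures (Sample-size considerations).** Inputs: 25 per arm, 17% loss by 12 months.
- Expected number remaining: 25 × 0.83 = 20.75. Binomial probability of 18 or more: 0.9505.
- SE of a mean, SD/√n: 0.200 SD at n = 25 and 0.236 SD at n = 18.
- SE of a proportion, √[p(1−p)/n], for 10%, 30% and 50%: 6.0%, 9.2%, 10.0% at n = 25; 7.1%, 10.8%, 11.8% at n = 18.

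All agree with the plan. They are standard errors for a single arm; none is given for a difference.

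**2. Half-widths of 90% intervals for arm differences.** With equal SDs and n per arm:
- Mean difference, 1.645 × √(2/n) × SD: 0.47 SD at n = 25 and 0.55 SD at n = 18.
- Proportion difference near 50%, 1.645 × √(2 × 0.25/n): 23 points at n = 25 and 27 points at n = 18.

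The two are on different scales, so their widths cannot be compared directly. Step 3 puts them on one scale.

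**3. Efficiency of a cut at 30 relative to comparing means.** The documents give no XQ mean, SD or distribution, so I assume normal scores and a location shift. With z = (30 − mean)/SD, efficiency = φ(z)² / [Φ(z)(1 − Φ(z))].

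| Assumed mean / SD | z | φ(z) | Φ(z) | Efficiency |
|---|---|---|---|---|
| 25 / 15 | 0.333 | 0.377 | 0.631 | 0.61 |
| 35 / 18 | −0.278 | 0.384 | 0.391 | 0.62 |
| 45 / 20 | −0.750 | 0.301 | 0.227 | 0.52 |

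The best case, a median split, gives 2/π = 0.64. In sample-size terms, 18 per arm analysed at the cutpoint is worth about 18 × 0.52 = 9 to 18 × 0.62 = 11 per arm analysed as means.

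In power terms (two-sided 0.10, 18 per arm, used only as a yardstick because the plan has no test):
- shift of 0.5 SD: 0.44 for means against 0.31 for a median split
- shift of 0.8 SD: 0.78 against 0.57

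**4. Hypothetical illustration of picking the best cutpoint.** No true difference, the three assumed distributions above clipped to 0-80, Newcombe 90% intervals, 20,000 simulated trials per setting. The cutpoint sets are mine, not the plan's.

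| Per arm | Cutpoints | Mean largest absolute difference | At least one interval excludes zero |
|---|---|---|---|
| 18 | 30 only | 11-13 points | 10-13% |
| 18 | 20, 30, 40, 50 | 19-20 points | 29-31% |
| 18 | 20 to 50 by 5 (seven) | 21-22 points | 37-38% |
| 25 | 30 only | 9-11 points | 10-11% |
| 25 | 20 to 50 by 5 (seven) | 18-19 points | 34-36% |

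**The case against.** The strongest reply is that little is lost. The primary-objective analysis already reports XQ means and SDs by arm with 90% intervals. The arms are independent, so anyone can compute the mean difference and its interval from those figures and the numbers of subjects. Exploratory mixed models on the undichotomized measures are planned as well. The proportion above a threshold is a legitimate quantity in its own right when the stated aim is to describe prevalence. As for the cutpoints, 30 is named in advance, the criterion for the rest is clinical relevance rather than separation of the arms, and differences are to be estimated for every dichotomized version. Looking at several thresholds is a reasonable thing for a pilot to do.

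Most of this stands, and it rules out three stronger readings that a reader might infer.
- *The trial discards over a third of its XQ information.* It does not: the continuous summaries are planned.
- *The arms are compared on the XQ only through dichotomized scores.* Not so, given the exploratory mixed models.
- *The plan will select the cutpoint with the largest difference.* The documents say nothing of the kind, so step 4 shows what such selection could do, not what is planned.

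What the reply does not meet is narrower. A difference that can be derived is not one the sponsor has undertaken to report. The mixed models are exploratory and their form is unspecified. The promise to estimate all dichotomized versions has no fixed denominator while the set is open.

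**Conclusion.** The point holds as a cheap improvement, not as an error that undermines the trial. Outside exploratory mixed models, the XQ arm differences planned with a 90% interval are proportion differences at cutpoints, and the cutpoints after 30 are unlisted. The plan already uses the more precise contrast for the EORTC scales.

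The efficiency of about 52-62% at a cut of 30 rests on assumed normality, a pure location shift, and assumed means of 25-45 with SDs of 15-20; other XQ distributions would give other values. The rise from 11-13 to 21-22 points with seven cutpoints at 18 per arm is hypothetical: it further assumes no true difference, my choice of cutpoints, and reporting of the largest.

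The documents also give no ground for insisting that 30 be the only cutpoint. In a descriptive pilot that would be a preference.

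**What to change.** In the analysis of secondary objective 1:
- Add the arm difference in mean overall XQ with a two-sided 90% interval at each time point, highlighting 12 months, which the plan already singles out for the secondary objectives.
- Keep XQ ≥ 30 as the lead cutpoint.
- List any further XQ cutpoints before outcome data by arm are viewed, report all of them, and label them exploratory. State that none will be carried into a larger trial because of its observed arm difference.

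The cost is a few sentences of plan text and one more row per table, with no new data. The downside is slightly less freedom to explore cutpoints.
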